General Study Design: The proposed study is a prospective, randomized, clinical trial with attention control under the direction of the dual PIs, a behavioral scientist and a virologist. The study team is also made up of investigators from infectious diseases, mind-body medicine, geriatrics, and biostatistics. Subjects will be randomized to participation in an 8-week group MBSR course as the study intervention or to the Health Enhancement Program (HEP) as the active control arm. The study population will consist of 120 individuals, 50 years old or older, long-term (5 years on ART or longer) HIV-infected adults with well-controlled plasma viremia. Randomization will be stratified to achieve balanced distribution between the groups based on gender and study site. The experimental group will participate in the 8-week MBSR course followed by six, once-per-month booster sessions, and the control group will participate in HEP, a validated group attention control condition for MBSR maintaining subjects inert to mindfulness, with additional monthly educational meetings for

six months. Both groups will be evaluated using two sets of measures: biological markers associated with chronic inflammation (IL-6, CRP, sCD14, d-dimer) and measures of psychosocial stress (anxiety, depression, fatigue, and mindfulness). Subjects will be assessed at three time points: baseline, 8 weeks (immediately after completion of MBSR intervention), and 6-months post MBSR course (immediately after completion of booster sessions). We will use mixed linear and structural equation model to test study hypotheses.

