Intervention: Mindfulness-Based Stress Reduction (MBSR) Course: The MBSR course will follow the approved curriculum by the University of Massachusetts Medical School. Participants will attend 8 weekly sessions, 2.5 hours each, and a 5 hour silent retreat during the 6th week of the program. Two cohorts of MBSR sessions (in concurrence with HEP attentive control sessions) will be conducted in groups of 30 subjects each. Formal mindfulness meditation methods taught in the MBSR course include: Body Scan Meditation (a supine meditation), Gentle Hatha Yoga (practiced with mindful awareness of the body), Sitting Meditation (mindfulness of breath, body, feelings, thoughts, and emotions), and Walking Meditation. Informal Mindfulness Meditation Practices (mindfulness in everyday life) include: 1) awareness of pleasant and unpleasant events, and, 2) deliberate awareness of routine activities and events such as eating, weather, walking, and interpersonal communication. Daily home assignments include a minimum of 30 minutes daily formal mindfulness practices and 5-15 minutes informal practice, 6 days per week for the entire duration of the course. Course sessions will consist of discussions oriented around weekly homework assignments, including an exploration of obstacles, and development of self-regulatory skills and capacities. Monitoring for completion of course assignments and mindfulness practice will also be recorded on a weekly basis using a daily online log. [name] will facilitate the MBSR course. She has taught MBSR to a wide range of patients and health professionals since 2006, and is a Certified MBSR Teacher, the highest level of teacher recognition by the University of Massachusetts Center for Mindfulness. After completion of the 8-week MBSR course, subjects will meet 6 times monthly for a 1-hour refresher session. A monthly online log will be used to record frequency of practice over this 6-month period. Subjects will receive biweekly email reminders to log their practice adherence.

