Potential Challenges, Proactive Measures, Alternative Strategies Given that we are recruiting subjects with an undetectable HIV viral load and therefore likely to be highly adherent to ARV medications, we expect high rates of adherence to study sessions. However, several procedures will be implemented to maximize attendance to the two study conditions. Subjects will not have their study baseline evaluation conducted at the time of consent, but be asked to return on a separate date to complete the baseline study evaluation to demonstrate their ability to adhere to scheduled appointments. Participants will be offered a round-trip metro card at each intervention session for travel expenses. Facilitators ([name] for MBSR and area experts for HEP) will be asked to provide information on subject attendance to the research coordinator (RC). Subjects will be asked to inform the facilitator if they plan to miss a session. For subjects that miss a session and do not contact the facilitator, the RC will reach out to the subject via email or phone.

Attention Control Arm: The Health Enhancement Program: Experts in mindfulness-based interventions argue for the use of an active control to eliminate the bias of the attention effect that can be encountered by the social interactions experienced by MBSR participants. MacCoon and colleagues have addressed this particular concern with the development of a validated attention control called the Health Enhancement Program (HEP).^{56,57} HEP is an active control that matches MBSR in non-specific factors, such as the amount of time participants interact, but does not include mindfulness practice as an active component. HEP instructors will be selected from experts in the areas covered: music, nutrition education, and, functional movement. The study's RC will coordinate HEP sessions and monitor attendance. Following the 8-week HEP protocol, subjects will meet monthly in 1.5-hour educational sessions to match the booster sessions of MBSR participants.

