Potential Challenges, Proactive Measures, Alternative Strategies: Although the HEP active control intervention provides the strongest RCT design, we are aware that it may also pose a challenge in observed outcomes if the effect size of our intervention is small. This is a plausible scenario for two reasons: (1) the attention effect of the active control intervention and (2) elements of the HEP intervention directly reducing psychosocial stress. To account for this possibility, statistical analysis will also include within subject differences. In addition, the sessions of HEP that could most influence stress reduction (i.e., physical activity)^{58,59} will be replaced by educational sessions. Elements such as the weather, and community illnesses associated with weather (i.e., colds, flu, etc.) may impact outcomes of the proposed study. To account for this potential impact, both arms of the study will take place concurrently. Both weekly sessions (one MBSR and another HEP) will take place during the same week in the exact same location (a conference room at Mount Sinai Hospital).

Participants and Recruitment: Subjects will be recruited at the Mount Sinai Health System in Manhattan, New York. In 2013, an integrated health system was created through the merger of Mount Sinai Medical Center and Continuum Health Partners. It is expected that the study will be able to recruit enough subjects at

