Aim 1: To assess the effect of MBSR on biomarkers of chronic inflammation in HIV-infected adults with well-controlled plasma viremia. The primary outcome for the analyses of treatment effectiveness will be IL-6 levels. We will use mixed linear models to assess the effect of the intervention on markers of inflammation. The model will include fixed effect terms for treatment group, time, and time-treatment interactions. In secondary analyses, we will similarly assess the effect of the intervention on secondary markers of inflammation (CRP, sCD14, d-dimer) using appropriate adjustments for multiple comparisons. If there are imbalances in patients’ characteristics across groups, statistical adjustment including these factors as covariates will be performed. All analysis will use an intent-to-treat principle. **Power Calculation:** Sample size calculations were based on the following assumptions: 1) mean baseline IL-6 of 2.0 pg/ml (SD:0.5)^{17,98}; 2) stable IL-6 levels in the control arm; 3) clinical significant effect of MBSR will be a net reduction of IL-6 of >0.5 pg/ml.^{98,99} Under these assumptions, a sample size of 100 patients (50 per group) will provide a power >80% using 2-sided test and a 0.05 significance level. One hundred and twenty study participants will be enrolled. Dropout rates reported in the literature for MBSR studies range significantly (range 0 to 48%, mean 10%). In order to lean on a conservative side a higher dropout rate of 15% is estimated for this study. With a 120 enrolled, a 15% dropout rate provides 102 completed participants. It is quite feasible to recruit 120 patients from this estimated eligible sample of 1,800 subjects at the three recruitment sites (requiring participation of ~7% of the eligible sample).

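### Both arms are taught in about four classes, but the Aim 1 model plans nothing for within-class correlation; pre-specify an ICC-inflated sensitivity analysis of the IL-6 contrast with a tipping point.

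*Combined protocol and SAP*

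**What the plan says.** All references are to the Combined protocol and SAP, part C (Approach).

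- **Size and allocation.** General Study Design: "The study population will consist of 120 individuals". Individuals are randomised to MBSR or HEP, stratified by gender and site. HEP is also a group programme.
- **Classes.** Intervention (MBSR Course): "Two cohorts of MBSR sessions (in concurrence with HEP attentive control sessions) will be conducted in groups of 30 subjects each". The Potential Challenges text for the attention control arm adds: "Both weekly sessions (one MBSR and another HEP) will take place during the same week in the exact same location". The HEP class size is not stated.
- **Teaching.** One named person "will facilitate the MBSR course". In the same section: "Course sessions will consist of discussions oriented around weekly homework assignments". For the control arm: "HEP instructors will be selected from experts in the areas covered: music, nutrition education, and, functional movement". The plan does not say whether the same HEP experts teach both cohorts.
- **Model.** Aim 1: "The model will include fixed effect terms for treatment group, time, and time-treatment interactions". Mixed models imply some random effect, but none is named. Covariates are provided for only where patient characteristics are imbalanced.
- **Power.** Aim 1, Power Calculation: "a sample size of 100 patients (50 per group) will provide a power >80% using 2-sided test and a 0.05 significance level". No ICC or design effect enters it.

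**The concern.** Individual randomisation makes patients independent at baseline. After that, each patient spends eight weeks in one class, with discussion inside that class. If IL-6 change is then more alike within a class than between classes of the same arm, the variance of the arm difference has a class component. A model with only patient-level variation leaves that component out. The standard error of the time-by-treatment contrast is then too small, the interval too narrow, and the 5% test rejects too often when MBSR has no effect.

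The planned output would not reveal this. Two classes per arm are too few to estimate the correlation, so the data cannot settle the matter afterwards. An ICC chosen once results are known could be picked to keep or lose significance.

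**Working it through.** **1. The plan's own figure.** Difference 0.5 pg/ml, SD 0.5, 50 per group, two-sided 0.05 (Aim 1). SE = 0.5 × sqrt(2/50) = 0.10, so z = 5 and power = Φ(5 − 1.96) = 99.9%. The claim of more than 80% is true on these inputs.

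**2. Class size.** 120/30 = 4 classes. With the plan's 15% dropout, m = 120 × 0.85/4 = 25.5 analysed per class, or 51 per arm.

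**3. SE multiplier.** The documents give no ICC; 0.01 and 0.05, for change from baseline, are assumptions.

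- DEFF = 1 + (m − 1) × ICC = 1 + 24.5 × ICC, giving 1.245 and 2.225.
- Both arms cluster: sqrt(DEFF) = 1.116 and 1.492.
- Only MBSR clusters: sqrt((DEFF + 1)/2) = 1.059 and 1.270.

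**4. True size of the nominal 5% test, and the planned p-value needed to stay below 0.05.** With multiplier k, size = 2 × (1 − Φ(1.96/k)) and required p = 2 × (1 − Φ(1.96 × k)).

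| Case | ICC | k | True size | Planned p must be below |
|---|---|---|---|---|
| No correlation | 0 | 1 | 5.0% | 0.05 |
| Both arms | 0.01 | 1.116 | 7.9% | 0.0287 |
| Both arms | 0.05 | 1.492 | 18.9% | 0.0035 |
| MBSR only | 0.01 | 1.059 | 6.4% | 0.0378 |
| MBSR only | 0.05 | 1.270 | 12.3% | 0.0128 |

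A simulation of the time-by-treatment contrast agrees. It used three visits, a person random intercept, a class effect after baseline only, classes of 26 and 25, and 20,000 trials. Sizes at 8 weeks/6 months were 5.0%/5.3% at ICC 0; 8.2%/7.8% and 19.5%/19.5% with both arms clustering; and 6.0%/6.5% and 12.7%/12.9% with MBSR only.

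**5. Tipping points, both arms clustering.** For a planned result with statistic z, significance is lost at ICC = ((z/1.96)² − 1)/24.5.

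- p = 0.03 (z = 2.170): 0.226/24.5 = 0.009
- p = 0.01 (z = 2.576): 0.727/24.5 = 0.030
- p = 0.005 (z = 2.807): 1.051/24.5 = 0.043

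With MBSR-only clustering, p = 0.01 survives to about ICC 0.059.

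**6. Power under clustering.** With SD 0.5 for change and 51 per arm, power for 0.5 pg/ml is 92% at ICC 0.05 and falls to 80% only at ICC 0.092. The plan gives no SD of change. If it were 0.707 (0.5 × sqrt 2, baseline-to-follow-up correlation r = 0, an assumption), the ICC must be rescaled. Change ICC = level ICC/(2(1 − r)), with equal visit variances and a class effect only after baseline. A level ICC of 0.05 is therefore 0.05 for change at r = 0.5 but 0.025 at r = 0. At 0.025, DEFF = 1 + 24.5 × 0.025 = 1.6125. The detectable difference at 80% power is 2.80 × 0.707 × sqrt(2 × 1.6125/51) = about 0.50 pg/ml, so power for 0.5 is about 80%.

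**7. Random class term as the primary analysis.** Four classes leave 2 df, or 1 df with cohort fixed. Power for 0.5 pg/ml at SD 0.5 would be 73% (2 df) or 31% (1 df) even at ICC 0, and 46% or 21% at ICC 0.05.

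**The case against.** The strongest reply is that clustering of a serum marker is not shown. One teacher takes the MBSR course, the arms run in the same weeks and place, and all frozen samples are assayed in a single run. A cohort effect shared by both arms cancels in the contrast. What remains is discussion within classes and silence on HEP staffing. The 19% also depends on an upper ICC that the documents do not supply. All of this stands: the point is conditional, and the relevant ICC is class within cohort, not the total within-class correlation.

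A second reply is that the plan's own effect would survive. With 0.5 pg/ml, SD 0.5 and 51 per arm, z = 5.05; divided by 1.492 it is 3.39, p = 0.0007. That is also correct. The issue matters for a smaller or borderline effect.

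A reader might infer three stronger things that the documents do not support:

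- **That the trial is underpowered.** It is not on the written inputs. Combining SD 0.707 with a change ICC of 0.05 gives 67% power and a detectable difference of 0.59 pg/ml, but that doubles the class variance (0.05 × 0.50 = 0.025 against 0.05 × 0.25 = 0.0125). With class variance matched, power is about 80%.
- **That a result which loses significance somewhere in the range depends on negligible class correlation.** A planned p of 0.01 withstands an ICC up to 0.030, which is not negligible.
- **That the plan excludes a class term.** The random effects are unstated, so the term is unplanned, not excluded.

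**Conclusion.** The concern holds as a conditional gap in the Aim 1 analysis. The plan delivers both interventions in about four classes and makes no provision for within-class correlation. If there is none, the planned test has its nominal 5% size. At assumed ICCs of 0.01 to 0.05 for change, true size is about 8% to 19% with both arms clustering and 6% to 12% with MBSR only.

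This rests on two HEP classes of similar size to the MBSR classes (inferred), 25.5 analysed per class, a normal reference distribution, and an ICC range that is not in the documents. The 6-month figures also assume that the same classes stay together for the monthly sessions, which the plan does not say. The sample size and power statement are not at fault. This should be addressed; confidence is medium, because the size of the problem depends on an unknown correlation.

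**What to change.** Keep the planned mixed model as primary and state its random effects. Before follow-up IL-6 results are analysed by arm, add a pre-specified sensitivity analysis of the IL-6 time-by-treatment contrast:

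- **Deciding case, both arms cluster:** multiply the SE by sqrt(DEFF), with DEFF = 1 + (m − 1) × ICC.
- **Supplementary case, MBSR only:** multiply it by sqrt((DEFF + 1)/2).
- **Definitions:** m is the number analysed per class; ICC is the class-within-cohort correlation of change from baseline, over an assumed range of 0.01 to 0.05.
- **Visits:** apply it at 8 weeks. Apply it at 6 months with the stated assumption that classes stay together.
- **Reporting:** give the interval across the range and the ICC at which significance is lost, and word the conclusion by that value.
- **Stated limits:** the multiplier treats the ICC as known, carries no degrees-of-freedom penalty for few classes, and does not separate the single MBSR teacher's effect from the arm effect.

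Do not make a random class term primary. Leave the power statement as it is. Any power or detectable-difference figure added under clustering should name its SD and match the class variance.

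The cost is one paragraph of analysis-plan text, wider sensitivity intervals and possibly a more cautious conclusion. No extra patients or classes are needed.

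### Monthly control sessions meant to match the MBSR boosters are set at 1.5 h against 1 h, so booster-phase group time is 9 h for HEP and 6 h for MBSR

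*Combined protocol and SAP*

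**What the plan says.** All references are to the combined protocol and SAP, section C (Approach).

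- **General Study Design** gives the schedule. The MBSR course is "followed by six, once-per-month booster sessions", and the control arm has HEP "with additional monthly educational meetings for" six months. The last assessment is at "6-months post MBSR course (immediately after completion of booster sessions").
- **Intervention: MBSR Course** describes the course as "8 weekly sessions, 2.5 hours each, and a 5 hour silent retreat". After it, "subjects will meet 6 times monthly for a 1-hour refresher session". A monthly online practice log runs over the same six months, and "Subjects will receive biweekly email reminders to log their practice adherence".
- **Attention Control Arm: The Health Enhancement Program** explains that an active control is used to remove attention bias. It says that HEP "matches MBSR in non-specific factors, such as the amount of time participants interact", without mindfulness practice. After the 8-week HEP protocol, "subjects will meet monthly in 1.5-hour educational sessions to match the booster sessions of MBSR participants". The section does not state the hours of the 8-week HEP course.
- The **Potential Challenges** paragraph that follows names the attention effect of the control as one reason why the observed effect might be small.
- **Aim 1** analyses IL-6, the primary outcome, with a mixed linear model containing group, time and their interaction.

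**The concern.** The control arm exists so that a difference between arms can be attributed to mindfulness and not to time spent in a supportive group. In the booster phase the plan gives the control sessions the stated purpose of matching the MBSR boosters, then makes each one half an hour longer. Number and timing agree, but length does not, and no section says why.

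What is at stake is the reading of the 6-month visit, which falls directly after the boosters and is one of two post-baseline assessments in the IL-6 model. If group contact itself has some benefit, the extra time sits in the comparator and would be expected to narrow the difference between arms. The plan already worries about dilution of this kind and replaces the HEP sessions most likely to reduce stress. Longer control sessions pull the other way. A null or reduced difference at 6 months would be slightly harder to interpret.

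**Working it through.** The plan states no total for booster hours, so there is no figure to reproduce. The check is sessions multiplied by hours per session.

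**Inputs**

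| Quantity | MBSR | HEP |
|---|---|---|
| Monthly sessions | 6 (General Study Design; Intervention) | 6 (inferred from monthly meetings over six months, General Study Design) |
| Length of each | 1 h (Intervention) | 1.5 h (Attention Control Arm) |
| 8-week course | 8 sessions of 2.5 h plus a 5 h retreat (Intervention) | not stated |

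The Intervention section's phrase about meeting six times monthly could be misread as six meetings in each month. General Study Design rules this out by specifying one per month.

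**Booster phase**

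- MBSR: 6 × 1.0 = 6 h
- HEP: 6 × 1.5 = 9 h
- Difference: 9 − 6 = 3 h, which is 0.5 h per month
- Ratio: 9 / 6 = 1.5

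**Whole programme**

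- MBSR course: 8 × 2.5 + 5 = 25 h
- MBSR total: 25 + 6 = 31 h
- HEP total: H + 9 h, where H is the unstated length of the HEP course
- The totals are equal when H + 9 = 31, so H = 22 h

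If H is assumed to equal the MBSR course at 25 h, HEP totals 25 + 9 = 34 h, which is 3 h or about 10% more than MBSR (3 / 31 = 0.097). If H is below 22 h, HEP totals less than MBSR. The sign of the overall difference therefore depends on a figure that the document does not give.

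**After alignment**

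- Both at 1 h: 6 h against 6 h
- Both at 1.5 h: 9 h against 9 h

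**The case against.** The best defence is that the sentence does not say the sessions match in length. Six monthly meetings are paired with six monthly boosters, and that may be all that was meant. The statement about interaction time describes HEP as a validated programme, and the monthly meetings are an addition after its 8 weeks. This reading is possible. It would turn a contradiction into an unexplained difference. It does not remove the point, because a reader of that paragraph would expect an attention control to match on time, and nothing says that the extra half hour was deliberate.

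The second defence is that session time is only part of attention. In the same six months MBSR subjects keep a practice log and receive email reminders every two weeks, and no HEP counterpart is stated. This stands. A reader might infer from 9 h against 6 h that the control arm receives more attention overall, in the booster phase or across the study. The document supports neither inference: the logs and reminders go to the other arm, and the HEP course hours are missing.

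The third defence is that no consequence has been shown. This also stands. The Potential Challenges paragraph recognises an attention effect from having an active control, but it gives no relation between session length and response. Nothing in the document links 30 minutes a month of group contact to IL-6.

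**Conclusion.** Wrong as written, minor. The plan states a matching aim for the monthly control sessions and then sets a length that does not meet it: 9 h of group time against 6 h over the booster phase. This rests on the two stated session lengths, which are explicit, and on six HEP meetings, which is inferred from the schedule. Confidence is high for the mismatch itself, but not for any effect on results.

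Three stronger readings should be resisted.

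- A reader might infer that the IL-6 comparison at 6 months is biased. No bias is demonstrated. The expected direction is against MBSR, and the size is unquantified and probably small.
- A reader might infer that the mismatch could never help to explain a result favouring MBSR. That is too absolute, because longer sessions might also burden HEP participants and affect their attendance or retention. The document does not settle this.
- A reader might take the restriction to the booster phase to mean that contact is equal at 8 weeks. The booster discrepancy does not bear on that visit, but equality there is unknown because the HEP course hours are not stated.

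The sample size, the endpoint and the analysis model are unaffected.

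**What to change.** Set one monthly session length for both arms and state it in both the Intervention section and the Attention Control Arm section, before the first cohort reaches the booster phase.

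The simplest choice is to shorten the HEP sessions to 1 h. This adds no burden for participants and removes 6 × 0.5 = 3 h of HEP session time per cohort. The alternative, 1.5 h in both arms, adds 3 h per MBSR participant. It also needs 2 × 6 × 0.5 = 6 more instructor hours over the two planned cohorts, if each cohort meets as one group.

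Neither option changes the sample size, the endpoint or the model. If the longer HEP session is deliberate, for example to offset the logs and reminders, the plan should at least say so and give the reason.

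### Do the undefined within-subject differences let an uncontrolled fall in IL-6 stand in for the comparison with HEP?

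*Combined protocol and SAP*

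**What the plan says.** In section C. Approach, the potential-challenges paragraph after the description of the HEP arm accepts that an active control is demanding: "it may also pose a challenge in observed outcomes if the effect size of our intervention is small". It gives two reasons: the attention that control participants receive, and HEP content that may itself lower stress. It offers two responses. The HEP sessions most likely to reduce stress "will be replaced by educational sessions". On the analysis side, "To account for this possibility, statistical analysis will also include within subject differences". No outcome, arm, time point, test or status follows, and the term does not recur.

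The Aim 1 paragraph sets out the main analysis. "The primary outcome for the analyses of treatment effectiveness will be IL-6 levels". On the mixed linear model: "The model will include fixed effect terms for treatment group, time, and time-treatment interactions". The only analyses it labels secondary concern the "effect of the intervention on secondary markers of inflammation (CRP, sCD14, d-dimer) using appropriate adjustments for multiple comparisons". Analysis is by intention to treat. The power calculation assumes stable IL-6 in controls and a net fall of more than 0.5 pg/mL with MBSR.

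Two other statements show why a concurrent comparison matters to this design. The Attention Control Arm paragraph reports that experts "argue for the use of an active control to eliminate the bias of the attention effect". On weather and community illness, the potential-challenges paragraph says: "To account for this potential impact, both arms of the study will take place concurrently".

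**The concern.** The sentence is attached to the one situation in which a fallback claim would be tempting: MBSR participants improve, HEP participants improve too, and the contrast is small. Change from baseline compared between arms is already the time-by-treatment term, so it adds nothing against that problem. That leaves before-after change within the MBSR arm as an apparent meaning.

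Such a change cannot separate MBSR from anything that moves both arms: attention, season, intercurrent illness, or simply time. It would discard the protections for which the plan chose an active, concurrent control. If a within-MBSR fall could be cited as an MBSR effect beside a null contrast, the trial could report benefit where there is none.

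**Working it through.** **Inputs from the plan (Aim 1).** Baseline IL-6 mean 2.0 pg/mL, SD 0.5; net effect 0.5 pg/mL; 50 per group; two-sided 0.05; 120 enrolled with 15% dropout.

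**Assumed, because the plan gives no figure.** Correlation rho between baseline and follow-up of 0.3, 0.5 or 0.7; a fall of 0.10 or 0.20 pg/mL common to both arms.

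**The plan's own figures.** The standard error of the difference is 0.5 × √(2/50) = 0.10, so the standardised effect is 0.5/0.10 = 5 and power is 99.9%. This satisfies the stated figure of more than 80%. Completers: 120 × 0.85 = 102, or 51 per arm.

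**Is the plan's worry real?** Yes. The SD of change is 0.5 × √(2(1 − rho)) = 0.592, 0.500 and 0.387. If MBSR falls by 0.5 and HEP by 0.25, the contrast is 0.25. Between-arm power with 51 per arm is then 57%, 71% and 90%.

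**What an MBSR-only before-after test would do with no MBSR-specific effect.** Paired t-test, n = 51, noncentrality = fall ÷ (SD of change/√51). At rho 0.5 and a fall of 0.10 this is 0.10/(0.500/7.141) = 1.43, giving 28.8%.

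| Shared fall (pg/mL) | rho 0.3 | rho 0.5 | rho 0.7 |
|---|---|---|---|
| 0.10 | 22% | 29% | 44% |
| 0.20 | 66% | 80% | 95% |

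The between-arm test on change rejects in about 5% of trials in every cell. By simulation, a significant within-MBSR fall occurs together with a non-significant contrast in 20-42% (fall 0.10) and 63-91% (fall 0.20) of trials.

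**If both arms are shown.** The arms are independent, so both within-arm tests are significant with the square of the tabulated probability. For a fall of 0.20 this is 0.658² = 0.43 to 0.951² = 0.90. For 0.10 it is 0.220² = 0.05 to 0.440² = 0.19. A large common change would often be visible; a small one usually would not.

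**A shared fall the plan's figures can size.** Entry requires IL-6 of at least 1.17 pg/mL. With a normal distribution of mean 2.0 and SD 0.5, the cut-off lies at (1.17 − 2.0)/0.5 = −1.66 and raises the screened mean by 0.053. Regression to the mean is 0.053 × (1 − rho), about 0.02 to 0.04 pg/mL. It is avoided if change is taken from the separate baseline draws. So this route does not reach even 0.10.

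**What the text commits to.** The Aim 1 model contains time and time-by-treatment terms. From these come each arm's change over time and the difference between those changes. Within-subject change in both arms is therefore already available from the planned model. It also answers the second stated worry, that HEP itself reduces stress, by showing whether HEP moved. The sentence names no single arm and says only that the analysis will also include these differences. The effect defined as clinically significant is a net one.

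**The case for a change.** The best case for acting is that nothing in the plan bars the bad use. The term is undefined and has no status. It sits outside the Aim 1 multiplicity provision: eight within-arm tests (four markers at two follow-ups) would carry a familywise error of up to 34% if independent. A net primary effect does not by itself forbid a second claim from within-arm change, and a clarifying sentence would cost nothing.

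Much of this stands. The term is undefined, the arithmetic is right, and a report presenting an MBSR-only fall as efficacy would be wrong. But that would be a fault of the report. The plan does not propose it, and the harmful meaning has to be inferred from one sentence in a paragraph about challenges.

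It could also be argued that a shared rise would hide a real benefit. With an MBSR-specific fall of 0.30 and a shared rise of 0.20, the within-MBSR test detects a fall in 22-44% of trials, against 72-97% for the between-arm test. This does not stand: the between-arm test is still run, so nothing is hidden.

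Nor is a restriction free of side effects. A rule that all conclusions about MBSR rest only on the Aim 1 contrast would, read literally, exclude the between-arm psychosocial comparisons and the mediation model in Aim 2.

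**Conclusion.** No change follows. The sentence leaves a supplementary analysis undefined, but the Aim 1 conclusion remains a between-arm one, based on the time-by-treatment term and a net fall. An analyst following the plan would take each arm's change from the same model, show both arms beside the contrast, and draw the MBSR conclusion from the contrast. A sentence saying so would add no better method and would alter no primary test, sample size or stated figure.

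The rates of 22-44% and 66-95% describe a misuse that the plan does not prescribe. They rest on assumed correlations of 0.3 to 0.7, on assumed shared falls of 0.10 and 0.20 pg/mL, and on only the MBSR arm being inspected. The plan itself assumes stable IL-6 in controls. The conclusion would differ if some passage allowed a within-arm fall to count as efficacy when the contrast is null; none does.
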